9.2.1 Selection of Study Population

Patients with gMG who are expected to start treatment with efgartigimod at enrolment or are within their first cycle of efgartigimod at enrolment will be eligible to enrol into the efgartigimod cohort. Patients with gMG who have not been exposed to efgartigimod and for whom it is not planned to start

treatment with efgartigimod at enrolment will be eligible to enrol into the non-efgartigimod cohort.

Physicians participating in the study will be instructed to invite all patients who meet study eligibility criteria to enrol until the enrolment period is closed.

Inclusion Criteria (efgartigimod cohort)

1. Patients diagnosed with gMG who are expected to start commercial efgartigimod at enrolment or who are within their first cycle of efgartigimod at enrolment
2. Have provided appropriate written informed consent

Inclusion Criteria (non-efgartigimod cohort)

3. Patients diagnosed with gMG who have not been exposed to efgartigimod and for whom it is not planned to start treatment with efgartigimod at enrolment
4. Have provided appropriate written informed consent

Exclusion Criteria

None

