9.3 Variables

Electronic case report forms (eCRFs) will be specifically designed for the collection of data from this study. An overview of the categories of study variables (raw data) to be collected for each enrolled patient is summarized in [Table 1](#). There may be some missing data if any assessments are not performed as part of normal clinical practice.

Table 1: Study Variables*

Category	Variables	Baseline	Follow up
Confirmation of eligibility, demographics, study status	
 Date of appropriate informed consent for study enrolment Eligibility assessment Demographic characteristics 	✓	
Past and current medical history	
 Relevant medical history including key co-morbidities (including past history of infections) 	✓	

Category	Variables	Baseline	Follow up
	
 Immune status (immunocompromised or immunocompetent) 	✓	✓
gMG Disease	
 Date of diagnosis 	✓	
	
 Criteria used for diagnosis of gMG 	✓	
	
 Antibody status (AChR, MuSK, anti-LRP4)/date 	✓	
	
 Clinical classification (Myasthenia Gravis Foundation of America recommendations) (Jaretzki, 2000) 	✓	✓
	
 Previous myasthenia crises 	✓	
	
 Thymectomy 
 Date Histology 	✓	✓
	
 MG-ADL questionnaire 	✓	✓
Renal function	
 Estimated glomerular filtration rate (eGFR) 	✓ (Most recent prior to initiation of efgartigimod therapy)	✓
gMG treatments in period from diagnosis prior to enrollment (excluding efgartigimod)	
 Drug name, start and stop dates 
 Acetylcholinesterase inhibitors Corticosteroids Other immunosuppressants (specify) Monoclonal antibodies (specify) Plasmapheresis/plasma exchange acute Plasmapheresis/plasma exchange chronic IVIg therapy acute IVIg therapy chronic Other 	✓	

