gMG treatments at or following enrollment (excluding efgartigimod)	
 Drug name, dose, start and stop dates 
 Acetylcholinesterase inhibitors Corticosteroids Other Immunosuppressants (specify) Monoclonal antibodies (specify) Plasmapheresis/plasma exchange acute Plasmapheresis/plasma exchange chronic IVIg therapy acute IVIg therapy chronic Other 	✓	✓

Category	Variables	Baseline	Follow up
Efgartigimod treatment	
 • Date of administration • Reason for interruption during cycle of treatment • Reason for permanent discontinuation whilst on study 	✓	✓
Other comedications at or following enrollment for conditions other than gMG	
 • Drug name, start and stop dates • Indication 	✓	✓
Live/attenuated vaccinations 2 months prior to enrollment to 2 months after last Vyvgart dose	
 • Live/attenuated vaccine 
 ○ Vaccine ○ Date 	✓	✓
Adverse Events (AEs)/Serious Adverse Events (SAEs)	
 • AEs, SAEs 		✓
Events of interest	See Table 2		✓

*All variables will be collected ONLY if available as part of routine clinical practice

A patient will be considered to be an efgartigimod exposed patient if he/she has received at least one dose of efgartigimod.

Additionally, taking into account the variable follow up time and time interval between cycles, the following will be measured for efgartigimod:

- Number of administrations per year
- Total duration of the exposure
- Total number of administrations

The exposure time window of efgartigimod is 56 days +/-3 days after the last dose.

Events of interest in this study will be pre-specified as per [Table 2](#) below.

Table 2: Pre-specified events of interest

Event of interest	Definition	Measurement
Serious infection	Any serious adverse event coded to the Medical Dictionary for Regulatory Activities (MedDRA) System Organ Class (SOC) of Infection and Infestation. See Section 11 for definition of Serious.	Proportion of patients who report serious infections during the course of the study in the efgartigimod treated cohort compared to the non-efgartigimod cohort. Incidence rate of serious infections per patient-years exposed in the efgartigimod treated cohort compared to the non-efgartigimod cohort.

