
AEs (serious and non-serious) in patients treated with monoclonal antibodies
	
Patients receiving monoclonal antibodies other than FcRn (e.g., adalimumab, tocilizumab, ixekizumab, rituximab) within 6 months prior to efgartigimod administration.
	
Proportion of AEs/SAEs reported in patients treated with monoclonal antibodies vs patients not treated with monoclonal antibodies in the efgartigimod cohort.
 
Incidence rate of AEs/SAEs per patient-years exposed in patients treated with monoclonal antibodies vs patients not treated with monoclonal antibodies in the efgartigimod cohort.

AEs (serious and non-serious) in patients treated with live attenuated vaccine
	
Patients receiving live/attenuated vaccine (e.g., live-attenuated flu vaccine, measles, mumps and rubella, polio, smallpox, chickenpox, yellow fever, Japanese encephalitis, shingles, rotavirus) in the period of 4 weeks prior to or 2 weeks after efgartigimod administration.
	
Proportion of AEs/SAEs reported in patients who have received live/attenuated vaccine vs patients who have not received live/attenuated vaccine in the efgartigimod cohort.
 
Incidence rate of AEs/SAEs per patient-years exposed in patients who have received live/attenuated vaccine vs patients who have not received live/attenuated vaccine in the efgartigimod cohort.

AEs (serious and non-serious) in patients with moderate to severe renal impairment
	
Moderate renal impairment: eGFR 30-59 mL/min/1.73 m² Severe renal impairment: eGFR < 30 mL/min/1.73 m²
	
Proportion of AEs/SAEs reported in patients with moderate renal impairment vs patients who have normal renal function in the efgartigimod cohort.
 
Incidence rate of AEs/SAEs per patient-years exposed in patients with moderate renal impairment vs patients who have normal renal function in the efgartigimod cohort.
 
Proportion of AEs/SAEs reported in patients with severe renal impairment vs patients who have normal renal function in the efgartigimod cohort.

		Incidence rate of AEs/SAEs per patient-years exposed in patients with severe renal impairment vs patients who have normal renal function in the efgartigimod cohort.
--	--	--

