9.5 Study Size

A sample size of 340 patients in each of the two cohorts is proposed (680 patients in total). Recruitment will be over a 5 year period and patients will be followed for 5 years from the time the last patient is enrolled. Thus maximum follow up will be 10 years.

The estimated prevalence rate for MG is 77.7 per million persons (range 15-179) and the estimated incidence rate is 5.3 per million person-years (range 1.7–21.3).

Myasthenia gravis occurs in both genders, at all ages, and in all races. However, for sample size calculations it is proposed to use the reported serious infection prevalence in MG patients.

Statistical analysis in this study will be descriptive and exploratory, and not aimed to confirm or reject predefined hypotheses.

Sample size calculation is driven by the precision of the estimated incidence proportion of serious infection assuming similar incidence proportion to the background.

In a population-based cohort study of 3823 MG patients ([Kassardjian 2020](#)) followed for a mean of 5.4 (Standard Deviation [SD]=3.8) years, 33.4% of patients experienced a serious infection which included both emergency department visits and hospitalisation with primary diagnosis of infection. In a retrospective chart review of 358 MG patients ([Prior 2018](#)) over a 10-year period, 19% of patients experienced infection. In the argenx-sponsored ADAPT+ study final analysis with 145 efgartigimod patients followed for a mean of 1.7 years (SD=0.7), 6.2% of patients experienced at least one serious infection (serious adverse event with SOC term "Infections and Infestations").

For the current study, serious infection incidence proportion is assumed to be 20% considering varied follow-up time and definitions of serious infection in the literature and argenx-sponsored trial.

The sample size needed to achieve a 5% precision (half-width) is presented in Table 3 below with the following assumptions:

- An incidence proportion of 20% for serious infections among patients receiving efgartigimod.
- Two-sided 95% exact binomial confidence limits based on the Clopper-Pearson method.

Table 3: Precision calculations for different incidence proportions

Number of Patients	Expected Incidence Proportion	Expected Number of Patients with Event*	Lower Limit of 95% Confidence Interval (CI) of Observed Incidence Proportion	Upper Limit of 95% CI of Observed Incidence Proportion
215	15%	32	10.5%	20.5%
245	18%	44	13.4%	23.4%
264	20%	52	15.3%	25.3%

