9.6 Data Management

Data will be collected and entered in eCRFs within a validated EDC system that is compliant with all regulatory requirements. The web-based EDC system aims to serve as a transparent tool to collect and manage data and track study progress at the patient level. Data in the EDC system are kept in a central location.

Site staff will be trained by the sponsor representative or delegate to perform the chart abstraction, including data entry and how to retrieve and respond to data queries in the EDC system. It is assumed that participating sites will be able to complete data entry into the eCRFs via the EDC system.

The sponsor representative or delegate will supervise and perform site management and monitoring as described in the study-specific monitoring plan. All participating sites will only have access to view and enter the data for their own patients. Only data required by the protocol for the purposes of the study should be collected.

The patient's routine clinical care treating physician has the ultimate responsibility for the collection and reporting of all clinical, safety, and treatment data entered into the eCRF and ensuring any other data collection forms (source documents) are accurate, authentic/original, attributable, complete, consistent, legible, timely, enduring, and available when required. The eCRFs must be electronically signed by the treating physician or by an authorized staff member to attest that the data contained on the eCRFs are true, complete, accurate and verifiable to source records. The argenx representative or delegate will inform sites when it is time for eCRF sign-off to occur.

Each site will maintain a Patient Identification list linking the patient to the Patient Identification within the EDC. Only the treating physician and/or authorised personnel will be able to identify the patient based on the Patient Identification list, which will be held only at the site.

The Investigator must permit study-related monitoring, audits, Institutional Review Board (IRB)/Independent Ethics Committee (IEC) review, and regulatory agency inspections and provide direct access to source data documents.

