Balance of the baseline measures, including age, MG-ADL score and region matched at enrollment and other demographic and disease characteristics, will be assessed. The imbalanced measures which are considered to be potential confounders based on clinical judgement will be added to the above base models as covariates. If a large number of imbalanced potential confounders are identified after the enrollment is complete, a propensity score method will be applied instead. More details will be given in the SAP.

Subgroup analyses will be performed using descriptive statistics on the subset of patients who remained on efgartigimod throughout the duration of the PASS. In addition, subgroup analyses of treatment cycle per year or administration per year (four administrations in one cycle if not interrupted), subgroup analyses of time since the last administration of efgartigimod prior to the event occurrence in intervals of every 4 weeks will be performed, and subgroup analysis of patients using efgartigimod as add-on or single treatment will be performed if sample size allows. Since one patient may have multiple same events with different time to the last administration, one patient may be assigned to multiple time intervals.

Events of Interest

Statistical analysis of malignancy and other events of interest will follow the same method as those for serious infections

Exploratory objectives

Descriptive statistics will be used to summarise the long-term safety of efgartigimod for specific subgroups. The number and percentage of patients with AEs/SAEs will be presented. The rate per person-year exposure with a 95% CI will be constructed using asymptomatic normal approximation. This will be done for the following subgroups:

- immunocompromised patients and immunocompetent patients.
- patients treated with monoclonal antibodies and patients not treated with monoclonal antibodies.
- patients who have received live/attenuated vaccine and patients who have not received live/attenuated vaccine.
- patients with moderate to severe renal impairment and patients with normal renal function or mild renal impairment.

Missing values

No imputation will be applied to occurrence of serious infection, malignancy or other safety events.

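### The monoclonal-antibody subgroup needs a six-month look-back, but drugs for non-gMG conditions are recorded only from enrolment, so some recently treated patients are counted as untreated

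*Protocol*

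**What the plan says.** All references are to the protocol.

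- **Subgroup definition (Section 9.3, Table 2).** The exposed group is "Patients receiving monoclonal antibodies other than FcRn (e.g., adalimumab, tocilizumab, ixekizumab, rituximab) within 6 months prior to efgartigimod administration". The definition does not depend on why the antibody was given.
- **Drugs before enrolment (Section 9.3, Table 1).** The only drug-history row that reaches back is headed "gMG treatments in period from diagnosis prior to enrollment (excluding efgartigimod", with the closing bracket following. It includes monoclonal antibodies, with start and stop dates.
- **Drugs for other conditions (Table 1).** The row is headed "Other comedications at or following enrollment for conditions other than gMG". It asks for drug name, indication and start and stop dates, and has no look-back.
- **Vaccines (Table 1).** This row does have a look-back: "Live/attenuated vaccinations 2 months prior to enrollment to 2 months after last Vyvgart dose".
- **Timing of the first dose (Section 9.2.1).** The efgartigimod cohort is "Patients diagnosed with gMG who are expected to start commercial efgartigimod at enrolment or who are within their first cycle of efgartigimod at enrolment".
- **Analysis (Section 9.7).** The comparison is between "patients treated with monoclonal antibodies and patients not treated with monoclonal antibodies".

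**The concern.** The definition in Table 2 cannot be applied with the data that Table 1 collects. Section 7 names eculizumab and rituximab as the antibodies used in gMG. The other three examples in Table 2 (adalimumab, tocilizumab, ixekizumab) would normally be recorded as drugs for other conditions, which is the row without a look-back. If such a course ended before enrolment, nothing in the database shows that it took place, and the patient and all of that patient's events are counted in the untreated group.

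This subgroup serves one of the four exploratory objectives in Section 8. Section 7 lists the use of efgartigimod with concomitant monoclonal antibodies as missing information in the risk management plan, because it has not been studied. Losing exposed patients weakens the little evidence the study can offer here. If the antibodies do raise risk, moving exposed patients into the reference group also pulls the contrast toward no difference.

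**Working it through.** The protocol states no figure on this point, so there is none to reproduce. The check has three steps.

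**1. Which antibody courses are recorded**

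| Antibody course | Row in Table 1 | Recorded? |
|---|---|---|
| For gMG, before enrolment | Prior gMG treatments, from diagnosis | Yes, with dates |
| For gMG, at or after enrolment | Current gMG treatments | Yes |
| Other condition, ongoing at enrolment | Other comedications | Yes, with start date |
| Other condition, started after enrolment | Other comedications | Yes |
| Other condition, stopped or last given before enrolment | None | No |

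The baseline items on medical history and immune status do not ask for drug names or dates, so they do not fill the last line.

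**2. How much of the window can be seen**

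Take six months as 182 days. For an efgartigimod dose on day *t* after enrolment, the part of the window in which non-gMG antibody use is collected is

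coverage = max(0, min(*t*, 182)) / 182.

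- Dose at or before enrolment: 0/182 = 0%
- Day 21 (fourth weekly infusion of Section 7 if the first is given on the day of enrolment): 21/182 = 12%
- Day 28: 28/182 = 15%
- Day 56: 56/182 = 31%
- Day 91: 91/182 = 50%
- Day 182 or later: 100%

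For the first cycle, almost the whole window is therefore unseen. The vaccine row shows the contrast: Table 2 needs four weeks before a dose, and Table 1 collects from two months before enrolment.

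**3. Possible size, on assumed frequencies**

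The cohort is N = 340 (Section 9.5). Assume that 1% to 5% of it stopped a non-gMG antibody in the six months before enrolment, and that a further 5% to 10% is correctly captured as treated.

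- Missed patients *m*: 0.01 × 340 = 3.4 to 0.05 × 340 = 17
- Captured patients *c*: 0.05 × 340 = 17 to 0.10 × 340 = 34
- Reference group as analysed, 340 − *c*: 323 to 306
- Exposed patients inside the reference group, *m*/(340 − *c*): 3.4/323 = 1.1% to 17/306 = 5.6%
- Share of truly exposed patients lost, *m*/(*m* + *c*): 3.4/37.4 = 9% to 17/34 = 50%

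The observed reference risk is [(n_ref − *m*) × r0 + *m* × r1]/n_ref, where n_ref = 340 − *c*. The true risks are again assumed, and missed patients are given the same risk as captured ones.

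- 20% against 30% (ratio 1.50): the observed ratio is 1.49 at the mild end. At *m* = 17 and n_ref = 306, the reference risk is (289 × 0.20 + 17 × 0.30)/306 = 20.6%, and the ratio is 1.46.
- 20% against 40% (ratio 2.00): the observed ratio is 1.98 at the mild end and 1.90 at the other.

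The dilution is small over the whole range. The loss of exposed patients can be large relative to the subgroup.

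**The case against.** The strongest reply is that the gap is narrow and the stakes are low. Antibodies for gMG are fully covered, and so are non-gMG antibodies still in use at enrolment. Only doses in about the first six months are affected, in a study with five to ten years of planned follow-up. The objective is exploratory and the analysis descriptive. The risk management plan item concerns concomitant use, whereas the patients missed had already stopped. All of this stands and limits the finding. The last point does not remove it, because Table 2 deliberately sets a wider six-month definition and that is what the analysis must apply.

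A second reply is that Section 9.3 introduces Table 1 as an overview, so the eCRF may ask for more. One could also argue that whatever Table 2 needs is by implication required. But the collection window is written into the row heading, as it is for vaccines, and an eCRF built from Table 1 would follow it. Section 9.6 adds: "Only data required by the protocol for the purposes of the study should be collected". At best the two tables point in different directions, and the text should settle which applies.

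A third reply is that Section 7 gives eculizumab and rituximab only as examples, so another antibody might be recorded as a gMG treatment. That is possible, but an antibody given for another disease would still belong in the comedication row.

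Finally, the frequencies are assumptions. That is so, and no weight should be put on them beyond showing the order of size.

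**Conclusion.** The concern holds. As written, an antibody for a non-gMG condition that was stopped or last given before enrolment is not recorded, although Table 2 counts it as exposure for doses within the following six months. The mismatch follows from the text alone and needs no numerical assumption.

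Its size is unknown. On the assumed 1% to 5%, it concerns 3 to 17 of 340 patients, and 9% to 50% of the truly exposed if 5% to 10% of the cohort is correctly captured. Bias in the reference risk is minor on the same assumptions. The main harm is a smaller exposed group.

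The primary objective, the sample size and the comparison between cohorts are unaffected. The change should still be made, because no analysis can recover the missing exposure. Section 9.9 does not list it as a limitation, and the ENCePP checklist (Annex 2) answers no to whether information bias, including misclassified exposure, is addressed.

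**What to change.** Add one baseline item to Table 1 and the eCRF: monoclonal antibodies for any indication, with drug name, indication, and start and stop (or last administration) dates, from six months before the first efgartigimod dose. Leave the row for other comedications as it is.

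Anchor the look-back on the first dose and not on enrolment, because patients may enrol within their first cycle. A patient enrolled 21 days after the first dose would otherwise have only 182 − 21 = 161 of the 182 days covered for that dose (88%). With the first-dose anchor, the window is complete for every dose.

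The cost is one eCRF item and a short look back through charts that sites already abstract (Section 9.4). No visit or test is added. Any patients already enrolled would need the same single chart check.

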In the EU RMP, use of efgartigimod in immunocompromised patients, in patients with moderate to severe renal impairment, in patients taking concomitant monoclonal antibodies and in patients receiving

live/attenuated vaccines is considered to be missing information as efgartigimod has not been studied in these patient populations. This post authorisation safety study will include these patient populations according to normal clinical practice. If these patients are enrolled into the study, the safety of efgartigimod will be assessed in these patient populations.

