9. RESEARCH METHODS

9.1 Study Design

This is a non-interventional, prospective, post authorisation safety study.

Patients with gMG who are expected to start treatment with efgartigimod at enrolment or are within their first cycle of efgartigimod at enrolment will be eligible to enrol into the efgartigimod cohort. Patients with gMG who have not been exposed to efgartigimod and for whom it is not planned to start treatment with efgartigimod at enrolment will be eligible to enrol into the non-efgartigimod cohort. It is anticipated that 340 patients will be enrolled in each cohort.

Patients will be treated and observed according to normal clinical practice. Participation in this study does not limit the physicians` clinical decision making as to the most appropriate treatment for the patient during the course of the study. No visits or investigations outside of normal clinical practice will be required. The enrolled patients will be followed prospectively until end of study participation, loss to follow up, consent withdrawal, or death, whichever comes first. All adverse events (AEs) will be collected throughout the duration of the study.

Enrolment of patients will be over a 5-year period. The follow up of patients will continue for 5 years from the time the last patient has been enrolled. Patients will be followed regardless of whether they continue or discontinue efgartigimod. Assuming a 5-year enrolment period this will allow for a maximum of 10 years of follow-up and a minimum of 5 years. A patient will be considered to be an efgartigimod exposed patient if he/she has received at least one dose of efgartigimod.

In order to minimise heterogeneity between the two cohorts, patients in the efgartigimod cohort will be matched at enrollment with a patient in the non-efgartigimod cohort for the following criteria:

- Age (\pm 5 years)
- Myasthenia Gravis -Activities of Daily Living (MG-ADL) score (0-5, 5-9, and >9) ([Wolfe, 1999](#))
- Region (within EU and within US)

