The study design includes an efgartigimod cohort and a comparator cohort of non-efgartigimod treated patients. The duration of the study is a maximum of 10 years (5 years of enrolment and 5 years of follow up). Over this time period, standard of care for the treatment of gMG is likely to evolve with the introduction of new medicinal products such as ultomiris (recently approved) and rozanolixizumab and zilucoplan (currently under review with an approval expected by end of 2023) and the potential for patients to switch treatments during this time. The comparator group, and indeed the efgartigimod group, will therefore be heterogenous in terms of treatments, thus limiting the interpretability of the results.

Furthermore, in countries where efgartigimod is marketed, it is likely that the efgartigimod cohort and the comparator cohort will differ in terms of disease severity with the more severe patients receiving efgartigimod. Thus, there will be an inherent selection bias. This could be solved by recruiting the comparator patients from countries where efgartigimod is not marketed. However, this will introduce further biases in terms of differing standards of care.

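### The antibody subgroup in Table 2 has no window after the efgartigimod dose, so an antibody started within the protocol's own 56-day exposure window leaves the patient in the untreated reference group (minor, exploratory subgroup only)

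*Protocol*

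**What the plan says.** Section 9.3 of the protocol states that events of interest are pre-specified in Table 2. The antibody row of that table defines the subgroup as "Patients receiving monoclonal antibodies other than FcRn (e.g., adalimumab, tocilizumab, ixekizumab, rituximab) within 6 months prior to efgartigimod administration". Its first measure is "Proportion of AEs/SAEs reported in patients treated with monoclonal antibodies vs patients not treated with monoclonal antibodies in the efgartigimod cohort", and the second is the matching incidence rate. Section 9.7 repeats the two-way split, "patients treated with monoclonal antibodies and patients not treated with monoclonal antibodies". No third category is given.

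Four other statements bear on this row:
- Section 9.3: "The exposure time window of efgartigimod is 56 days +/-3 days after the last dose".
- Section 7 lists as missing information the use of efgartigimod "in patients taking concomitant monoclonal antibodies".
- Section 9.1: "Patients will be followed regardless of whether they continue or discontinue efgartigimod".
- Section 9.9 expects treatment practice to change and notes "the potential for patients to switch treatments during this time".

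The next row of Table 2, on live vaccines, looks in both directions: "in the period of 4 weeks prior to or 2 weeks after efgartigimod administration".

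**The concern.** The subgroup is meant to inform a named gap in the EU Risk Management Plan, the safety of efgartigimod together with a monoclonal antibody. A reference group for that question should hold patients without the combination. As defined, it can hold two kinds of patient who do not belong there:

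- a patient who stops efgartigimod for good and then starts an antibody, including one who starts while still inside the 56-day window;
- a patient whose only antibody was an FcRn antibody, because the definition excludes that class and the split leaves only one other place to go.

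If such patients share the raised risk of the combination, the contrast shrinks. For a safety question that is an error in the reassuring direction.

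**Working it through.** The plan gives no figure for this contrast, so there is none to reproduce. The check is one of definitions, followed by an illustration of size.

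**Definitions side by side**

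1. *Antibody before a dose.* The window attaches to any efgartigimod administration, not only the first. An antibody started between cycles is captured if another efgartigimod dose follows within 6 months. There is no gap here.
2. *Antibody after the final dose, within 56 days.* No later efgartigimod administration exists, so the 6-month look-back can never be met. By section 9.3 the patient is still exposed to efgartigimod, so the use is concomitant. Table 2 does not count it.
3. *Antibody after the final dose, beyond 56 days.* This is sequential use, not combined use. The patient remains in the efgartigimod cohort, because one dose makes a patient exposed, and remains in follow-up, labelled as untreated while on an antibody.
4. *FcRn antibody only.* Section 9.2.1 has no exclusion criteria, so such a patient can enrol. The patient does not meet the definition, yet the untreated label does not describe that patient.
5. *Vaccine row.* It looks 2 weeks forward, so a forward window is already part of the design.

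**Size**

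Let R be the true rate ratio for antibody-treated versus untreated, S the rate in the misplaced person-time relative to truly untreated time, and c the share of reference person-time that is misplaced. Then

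observed ratio = R / (1 + c(S − 1)).

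The documents give none of R, S or c, so all three are assumptions. Take S = R at first.

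*Only combined time counted as misplaced.* Each switcher contributes at most 56 days. Against the 5-year minimum follow-up of section 9.1, 56 / (5 × 365.25) = 3.07%.
- 15% switchers (assumed): c = 0.15 × 3.07% = 0.46%. With R = 1.50: 1.50 / (1 + 0.0046 × 0.5) = 1.497.
- 30% switchers (assumed): c = 0.92%. 1.50 / (1 + 0.0092 × 0.5) = 1.493.

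*All follow-up after a switch counted.* Here c could be anything, so a range is shown:

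| c | R = 1.5 reads | R = 2.0 reads |
|---|---|---|
| 5% | 1.46 | 1.90 |
| 10% | 1.43 | 1.82 |
| 20% | 1.36 | 1.67 |
| 30% | 1.30 | 1.54 |

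*Direction.* If S = 1 the observed ratio does not change. If S is below 1, for example because switchers are now off efgartigimod and at lower risk, the ratio is exaggerated instead.

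*Denominator.* If the patient-years exposed in Table 2 are limited to the 56-day window, late events after a switch leave the rate but not the proportion. The combined days could then be a larger share of a smaller denominator. Antibodies started inside the window remain misplaced in both measures.

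**The case against.** The backward window fits the wording of the exploratory objective in section 8, which concerns giving efgartigimod to patients who are already on an antibody. That explains the choice, but section 7 names concomitant use, and an antibody started two weeks after the last dose is concomitant by the protocol's own window.

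The reference group is not separately defined, and its label read literally would leave FcRn-antibody patients and switchers out of both groups. Placing them could then be called a detail for the SAP, to which Annex 2 defers exposure details. This is fair as far as it goes. But section 9.3 fixes the definition in the protocol and the split has two sides only, so the default is the reference group. On either reading, definition and label do not match. The FcRn exclusion itself has an evident purpose, since efgartigimod acts by binding FcRn; only where those patients end up is in question.

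A reader might infer that the reference group is heavily contaminated with the combination under study. The documents do not support that. Years on an antibody after efgartigimod has been stopped are sequential exposure, combined for about 56 days at most. The switching share, the antibody effect and the risk of switchers are given nowhere, and no product is identified as an FcRn antibody.

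A reader might also infer that the vaccine row leaves most of the exposure window uncovered. That is so only after a final dose. Between doses, 14 days forward plus 28 days back cover any gap up to 42 days, and in an 8-week gap 56 − 42 = 14 of 56 days (25%) are uncovered. Nor does it contradict Table 2 that Table 1 collects vaccines over a longer period.

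**Conclusion.** The point holds as a small mismatch in a stated rule. Followed as written, Table 2 misses concomitant antibody use that begins after the final efgartigimod dose, and by complement puts those patients, and those with only an FcRn antibody, in the reference group. The size is unknown: very small if only combined time counts against full follow-up, larger if all time after a switch counts. A shift towards no difference is not established; it rests on the assumption that switchers carry the raised risk. The subgroup is exploratory and descriptive, so the severity is minor. The primary comparison, sample size and power are unaffected.

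**What to change.** For analysis classification only, reword the antibody row of Table 2:

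- Define concomitant antibody use as an antibody given within 6 months before an efgartigimod dose or within 56 days after one.
- Start antibody-treated person-time when both exposures are first present, and end untreated person-time at the first antibody dose. Time before the combination then stays out of the treated group, and time after a late switch stays out of the reference group.
- Keep patients with an FcRn antibody in the same windows out of the reference group and show them as a separate category.

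Optionally, list live vaccines given on days 15 to 56 after a dose, and not within 4 weeks before another dose, separately from those counted as not received. The existing vaccine group need not change.

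The data for the forward window are already in Table 1: start and stop dates of gMG treatments and other comedications at follow-up, and live vaccines to 2 months after the last dose. The costs are one or two small extra categories and time-split programming. Ending untreated time at a switch may censor informatively if an adverse event prompted the switch; reporting the uncensored result alongside allows that to be checked.
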